6.2.4.1. BFI Item 3 and PROMIS Weekly Assessment Windows

Daily assessments of BFI item 3 and assessment of PROMIS will be assigned to a single weekly analysis time point according to the table below.

Table 3 BFI Item 3 and PROMIS Weekly Assessment Windows

Analysis Timepoint	Analysis Window		
	Beginning Timepoint	Ending Timepoint	Special Rules for Handling Overlapping Timepoints
Week 52	Week 52 (Visit 15) visit date – 7 days	Week 52 (Visit 15) visit date – 1 day	
Week 51	Week 52 (Visit 15) visit date – 14 days	Week 52 (Visit 15) visit date – 8 days	If assessment falls into Week 51/Week 50/Week 49 and Week 48, assign assessment as Week 48. If assessment date is less than Week 48 (Visit 14) visit date, assign a relevant timepoint less than Week 48.
Week 50	Week 52 (Visit 15) visit date – 21 days	Week 52 (Visit 15) visit date – 15 days	
Week 49	Week 52 (Visit 15) visit date – 28 days	Week 52 (Visit 15) visit date – 22 days	
Week 48	Week 48 (Visit 14) visit date – 7 days	Week 48 (Visit 14) visit date – 1 day	
Week 47	Week 48 (Visit 14) visit date – 14 days	Week 48 (Visit 14) visit date – 8 days	If assessment falls into Week 47/Week 46/Week 45 and Week 44, assign assessment as Week 44. If assessment date is less than Week 44 (Visit 13) visit date, assign a relevant timepoint less than Week 44.
Week 46	Week 48 (Visit 14) visit date – 21 days	Week 48 (Visit 14) visit date – 15 days	
Week 45	Week 48 (Visit 14) visit date – 28 days	Week 48 (Visit 14) visit date – 22 days	
Week 44	Week 44 (Visit 13) visit date – 7 days	Week 44 (Visit 13) visit date – 1 day	
Week 43	Week 44 (Visit 13) visit date – 14 days	Week 44 (Visit 13) visit date – 8 days	If assessment falls into Week 43/Week 42/Week 41 and Week 40, assign assessment as Week 40. If assessment date is less than Week 40 (Visit 12) visit date, assign a relevant timepoint less than Week 40.
Week 42	Week 44 (Visit 13) visit date – 21 days	Week 44 (Visit 13) visit date – 15 days	
Week 41	Week 44 (Visit 13) visit date – 28 days	Week 44 (Visit 13) visit date – 22 days	
Week 40	Week 40 (Visit 12) visit date – 7 days	Week 40 (Visit 12) visit date – 1 day	
Week 39	Week 40 (Visit 12) visit date – 14 days	Week 40 (Visit 12) visit date – 8 days	If assessment falls into Week 39/Week 38/Week 37 and Week 36, assign assessment as Week 36.
Week 38	Week 40 (Visit 12) visit date – 21 days	Week 40 (Visit 12) visit date – 15 days	

Analysis Timepoint	Analysis Window		
	Beginning Timepoint	Ending Timepoint	Special Rules for Handling Overlapping Timepoints
Week 37	Week 40 (Visit 12) visit date – 28 days	Week 40 (Visit 12) visit date – 22 days	If assessment date is less than Week 36 (Visit 11) visit date, assign a relevant timepoint less than Week 36.
Week 36	Week 36 (Visit 11) visit date – 7 days	Week 36 (Visit 11) visit date – 1 day	
Week 35	Week 36 (Visit 11) visit date – 14 days	Week 36 (Visit 11) visit date – 8 days	If assessment falls into Week 35/Week 34/Week 33 and Week 32, assign assessment as Week 32. If assessment date is less than Week 32 (Visit 10) visit date, assign a relevant timepoint less than Week 32.
Week 34	Week 36 (Visit 11) visit date – 21 days	Week 36 (Visit 11) visit date – 15 days	
Week 33	Week 36 (Visit 11) visit date – 28 days	Week 36 (Visit 11) visit date – 22 days	
Week 32	Week 32 (Visit 10) visit date – 7 days	Week 32 (Visit 10) visit date -1 day	
Week 31	Week 32 (Visit 10) visit date – 14 days	Week 32 (Visit 10) visit date – 8 days	If assessment falls into Week 31/Week 30/Week 29 and Week 28, assign assessment as Week 28. If assessment date is less than Week 28 (Visit 9) visit date, assign a relevant timepoint less than Week 28.
Week 30	Week 32 (Visit 10) visit date – 21 days	Week 32 (Visit 10) visit date – 15 days	
Week 29	Week 32 (Visit 10) visit date – 28 days	Week 32 (Visit 10) visit date – 22 days	
Week 28	Week 28 (Visit 9) visit date – 7 days	Week 28 (Visit 9) visit date – 1 day	
Week 27	Week 28 (Visit 9) visit date – 14 days	Week 28 (Visit 9) visit date – 8 days	If assessment falls into Week 27/Week 26/Week 25 and Week 24, assign assessment as Week 24. If assessment date is less than Week 24 (Visit 8) visit date, assign a relevant timepoint less than Week 24.
Week 26	Week 28 (Visit 9) visit date – 21 days	Week 28 (Visit 9) visit date – 15 days	
Week 25	Week 28 (Visit 9) visit date – 28 days	Week 28 (Visit 9) visit date – 22 days	
Week 24	Week 24 (Visit 8) visit date – 7 days	Week 24 (Visit 8) visit date – 1 day	
Week 23	Week 24 (Visit 8) visit date – 14 days	Week 24 (Visit 8) visit date – 8 days	If assessment falls into Week 23/Week 22/Week 21 and Week 20, assign assessment as Week 20. If assessment date is less than Week 20 (Visit 7) visit date,
Week 22	Week 24 (Visit 8) visit date – 21 days	Week 24 (Visit 8) visit date – 15 days	
Week 21	Week 24 (Visit 8) visit date – 28 days	Week 24 (Visit 8) visit date – 22 days	

Analysis Timepoint	Analysis Window		
	Beginning Timepoint	Ending Timepoint	Special Rules for Handling Overlapping Timepoints
			assign a relevant timepoint less than Week 20.
Week 20	Week 20 (Visit 7) visit date – 7 days	Week 20 (Visit 7) visit date -1 day	
Week 19	Week 20 (Visit 7) visit date – 14 days	Week 20 (Visit 7) visit date – 8 days	If assessment falls into Week 19/Week 18/Week 17 and Week 16, assign assessment as Week 16.
Week 18	Week 20 (Visit 7) visit date – 21 days	Week 20 (Visit 7) visit date – 15 days	
Week 17	Week 20 (Visit 7) visit date – 28 days	Week 20 (Visit 7) visit date – 22 days	If assessment date is less than Week 16 (Visit 6) visit date, assign a relevant timepoint less than Week 16.
Week 16	Week 16 (Visit 6) visit date – 7 days	Week 16 (Visit 6) visit date – 1 day	
Week 15	Week 16 (Visit 6) visit date – 14 days	Week 16 (Visit 6) visit date – 8 days	If assessment falls into Week 15/Week 14/Week 13 and Week 12, assign assessment as Week 12.
Week 14	Week 16 (Visit 6) visit date – 21 days	Week 16 (Visit 6) visit date – 15 days	
Week 13	Week 16 (Visit 6) visit date – 28 days	Week 16 (Visit 6) visit date – 22 days	If assessment date is less than Week 12 (Visit 5) visit date, assign a relevant timepoint less than Week 12.
Week 12	Week 12 (Visit 5) visit date – 7 days	Week 12 (Visit 5) visit date – 1 day	
Week 11	Week 12 (Visit 5) visit date – 14 days	Week 12 (Visit 5) visit date – 8 days	If assessment falls into Week 11/Week 10/Week 9 and Week 8, assign assessment as Week 8.
Week 10	Week 12 (Visit 5) visit date – 21 days	Week 12 (Visit 5) visit date – 15 days	
Week 9	Week 12 (Visit 5) visit date – 28 days	Week 12 (Visit 5) visit date – 22 days	If assessment date is less than Week 8 (Visit 4) visit date, assign a relevant timepoint less than Week 8.
Week 8	Week 8 (Visit 4) visit date – 7 days	Week 8 (Visit 4) visit date – 1 day	
Week 7	Week 8 (Visit 4) visit date – 14 days	Week 8 (Visit 4) visit date – 8 days	If assessment falls into Week 7/Week 6/Week 5 and Week 4, assign assessment as Week 4. If assessment date is less than Week 4 (Visit 3) visit date, assign a relevant timepoint less than Week 4.
Week 6	Week 8 (Visit 4) visit date – 21 days	Week 8 (Visit 4) visit date – 15 days	
Week 5	Week 8 (Visit 4) visit date – 28 days	Week 8 (Visit 4) visit date – 22 days	
Week 4	Week 4 (Visit 3) visit date – 7 days	Week 4 (Visit 3) visit date – 1 day	

Analysis Timepoint	Analysis Window		
	Beginning Timepoint	Ending Timepoint	Special Rules for Handling Overlapping Timepoints
Week 3	Week 4 (Visit 3) visit date – 14 days	Week 4 (Visit 3) visit date – 8 days	If assessment falls into Week 3/Week 2/Week 1 and Baseline (Week 0) or Screening, assign assessment as Baseline (Week 0) or Screening.
Week 2	Week 4 (Visit 3) visit date – 21 days	Week 4 (Visit 3) visit date – 15 days	
Week 1	Week 4 (Visit 3) visit date – 28 days	Week 4 (Visit 3) visit date – 22 days	
Baseline (Week 0)	Date of first dose of study treatment – 7 days	Date of first dose of study treatment – 1 day	
Screening	N/A	Date of first dose of study treatment – 8 days	

6.2.4.2. Medication Assessment Windows

For the reporting of medication use and changes in medication use (e.g. change in OCS dose and change in immunosuppressive and/or cytotoxic HES therapy) will be assigned to a 4-weekly analysis time point according to the table below.

Table 4 Medication Assessment Windows

Reporting Period	First Day Included	Last Day Included
Pre-treatment	Medication is taken on the date of first dose of IP (Day 1)	
Weeks 0-4 (Baseline)	Day after day of first dose	28 days after day of first dose
Weeks 4-8	29 days after day of first dose	56 days after day of first dose
Weeks 8-12	57 days after day of first dose	84 days after day of first dose
Weeks 12-16	85 days after day of first dose	112 days after day of first dose
Weeks 16-20	113 days after day of first dose	140 days after day of first dose
Weeks 20-24	141 days after day of first dose	168 days after day of first dose
Weeks 24-28	169 days after day of first dose	196 days after day of first dose
Weeks 28-32	197 days after day of first dose	224 days after day of first dose
Weeks 32-36	225 days after day of first dose	252 days after day of first dose
Weeks 36-40	253 days after day of first dose	280 days after day of first dose
Weeks 40-44	281 days after day of first dose	308 days after day of first dose

Reporting Period	First Day Included	Last Day Included
Weeks 44-48	309 days after day of first dose	336 days after day of first dose
Weeks 48-52	337 days after day of first dose	364 days after day of first dose

6.2.5. Multiple measurements at One Analysis Time Point

In the case of any questionnaires or eCOA endpoint data which reflect multiple assessments or results on a single study day, the earliest date/time completed score on each given day (or analysis window) will be taken.

For ECG, if multiple assessments are recorded on the same day, the mean of the parameters recorded in the multiple assessments will be used in the derivation of any summary statistics for that ECG parameter. For spirometry measures, the best of the multiple assessments [as determined by the Spirometry vendor technician] will be used for summary statistics [identified within the SDTM datasets using SUPPRE.QVAL='Y' where QNAM='BERESFL']. For all other measurements, unless specified, if there are multiple assessments are taken at a single visit the first assessment will be used in any derivation of summary statistics. All values will be presented in listings.

For laboratory tests, if more than one assessment is taken on the same day, the test from a central laboratory will be taken over the test from a local laboratory. Participants having both High and Low values for Normal Ranges at any post-baseline visits for safety parameters will be counted in both the High and Low categories of “Any visit post-baseline” row of related summary tables. This will also be applicable to relevant Potential Clinical Importance summary tables, if applicable.

6.2.6. Handling of Partial Dates

Element	Reporting Detail
General	
 Partial dates will be displayed as captured in participant listing displays. However, where necessary, display macros may impute dates as temporary variables for sorting data in listings only. In addition, partial dates may be imputed for 'slotting' data to study phases or for specific analysis purposes as outlined below. Imputed partial dates will not be used to derive study day, time to onset or duration (e.g., time to onset or duration of adverse events).
HES Flare and Adverse Events	
 Any partial dates for HES flare and adverse events will be raised to data management. If the full date cannot be ascertained, the following assumptions will be made: If the partial date is a start date, a '01' will be used for the day and 'Jan' will be used for the month. However, if this imputation results in a date prior to the first dose of study treatment and the event could possibly have occurred during treatment from the partial information, then the date of the first dose of study treatment will be assumed to be the start date.

Element	Reporting Detail
	
 ○ The event will then be considered to start on-treatment (worst case). ○ If the partial date is a stop date, a '28/29/30/31' will be used for the day (dependent on the month and year) and 'Dec' will be used for the month. ○ Completely missing start or end dates will remain missing, with no imputation applied. Consequently, time to onset and duration of such events will be missing. 
The recorded partial date will be displayed in listings.

Concomitant Medications	
 ○ Partial dates for any concomitant medications recorded in the CRF will be imputed using the following convention: 
 ○ If the partial date is a start date, a '01' will be used for the day and 'Jan' will be used for the month ○ If the partial date is a stop date, a '28/29/30/31' will be used for the day (dependent on the month and year) and 'Dec' will be used for the month. 
The recorded partial date will be displayed in listings.

6.2.7. Laboratory Parameters

If a laboratory value which is expected to have a numeric value for summary purposes has a non-detectable level reported in the database, where the numeric value is missing, but instead a character value starting with '<x' or '>x' (or indicated as less than x or greater than x in the comment field) is present, a numeric value will be imputed; the number of significant digits in the observed value will be used to determine how much to add or subtract to impute the corresponding numeric value:

- Example 1: 2 significant digits = '< x' imputed as $x - 0.01$
- Example 2: 1 significant digit = '> x' imputed as $x + 0.1$
- Example 3: 0 significant digits = '< x' imputed as $x - 1$

Laboratory values with missing values due to being below the limit of quantification (BLQ) for that parameter will have a value imputed as half the lower limit of quantification for that measure (i.e. the lowest observed value for that measure within the entire study database).

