1.1. Objectives, Estimands and Endpoints

Objectives	Endpoints
Primary	

 To evaluate the efficacy of mepolizumab SC given every 4 weeks in participants aged 6 to 17 years with HES. 	
 Frequency of HES flares over the 52-week study treatment period.
Secondary	

 To assess the effect of mepolizumab SC given every 4 weeks on the change in oral corticosteroid (OCS) dose in participants aged 6 to 17 years with HES that are taking OCS at baseline. 	
 Change in the mean daily OCS dose (prednisone/prednisolone or equivalent) from Weeks 0 to 4 to Weeks 48 to 52. Reduction of $\geq 50\%$ in mean daily OCS dose (prednisone/prednisolone or equivalent) from Weeks 0 to 4 compared with Weeks 48 to 52. Achieving a mean daily OCS dose (prednisone/prednisolone or equivalent) of ≤ 7.5 mg during Weeks 48 to 52.

 To assess the effect of mepolizumab SC given every 4 weeks on the change in oral corticosteroid (OCS) dose in participants aged 6 to 17 years with HES. 	
 Achieving a mean daily OCS dose (prednisone/prednisolone or equivalent) of ≤ 7.5 mg during Weeks 48 to 52.

 To assess the efficacy of mepolizumab SC given every 4 weeks on fatigue in participants aged 12 to 17 years with HES. 	
 Change from baseline in fatigue severity based on weekly average score of Brief Fatigue Inventory (BFI) item 3 (worst level of fatigue during past 24 hours) for Week 52.

 To evaluate the immunogenicity of mepolizumab SC given every 4 weeks in participants aged 6 to 17 years with HES. 	
 Occurrence of anti-drug antibodies (ADA) and neutralising antibodies (NAb).

 To assess the effect of long-term use of mepolizumab SC on a pharmacodynamics (PD) marker in participants aged 6 to 17 years with HES. 	
 Ratio to baseline in absolute blood eosinophil count at discrete time points during the 52-week study treatment period.

 To assess the pharmacokinetics (PK) of mepolizumab SC in participants aged 6 to 17 years with HES. 	
 Mepolizumab plasma concentration at discrete time points during the 52-week study treatment period.

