6.1.2. Demographic and Baseline Characteristics

The demographic characteristics including age, gender, height/weight, BMI at screening, race, race detail will be summarized. In addition, the following age categories will be summarized: 6-11 and 12-17 based on the Enrolled Analysis Set. Past medical conditions and current medical conditions as of screening will be summarized respectively.

A summary of baseline HES therapy, duration of HES, number of flares 12 months prior to screening, and baseline OCS doses will be summarized (refer section 6.2.1). The number of L-HES patients based on T-cell profile data and baseline laboratory information (including CD3-CD4+, Interleukin-5, Immunoglobulin E and blood eosinophil count data) will be summarized

If the summary of demographics meets the criteria for de-identification, as described in the relevant procedural document, a de-identification version will be produced.

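### SAP 6.2.7 takes the lowest value in the study database as the assay's quantification limit, and does not say which of its two imputation rules governs a '<x' laboratory result

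*SAP*

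**What the plan says.** SAP 6.2.7 (Laboratory Parameters) has two rules for laboratory results that lack a number.

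- **Shift rule.** It applies to a non-detectable level "where the numeric value is missing, but instead a character value starting with '<x' or '>x", or where a comment gives the same information. The imputed value is x moved by one unit, and "the number of significant digits in the observed value will be used to determine how much to add or subtract". Three examples give shifts of 0.01, 0.1 and 1 for two, one and zero digits.
- **Half-limit rule.** A value missing because it is below the limit of quantification is "imputed as half the lower limit of quantification for that measure". The limit is then explained in brackets as "the lowest observed value for that measure within the entire study database".

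The section names no analyte, gives no assay limit, exempts no measure and sets no order between the rules.

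Two other places show where imputed values may be used. SAP 6.1.2 states that "baseline laboratory information (including CD3-CD4+, Interleukin-5, Immunoglobulin E and blood eosinophil count data) will be summarized". SAP 1.1 lists a secondary pharmacodynamic endpoint: "Ratio to baseline in absolute blood eosinophil count at discrete time points during the 52-week study treatment period".

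**The concern.** A quantification limit is a property of the assay. The smallest number that happens to occur among the study's participants is a property of the sample. The two coincide only if some participant is measured exactly at the limit. Otherwise the study minimum is the larger, and half of it may be a value that the laboratory has already ruled out for that specimen.

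Separately, a result reported as '<x' with no number can meet both triggers. Two programmers who each follow the SAP could then impute different values for the same specimen.

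The stake is the accuracy and reproducibility of laboratory summaries. The gap between study minimum and assay limit matters most for measures with few results. In the Protocol's Schedule of Activities, IL-5 and total IgE are taken once, at Visit 2, and about 15 participants are planned.

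**Working it through.** **Inputs.** Both rules and the three examples come from SAP 6.2.7. The documents give no assay limits, so the values of x and the multiples m below are assumptions chosen to show the range.

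**1. Reproducing the SAP's examples.** Let d be the number of decimal places in x and take the shift as u = 10^(−d). Then d = 2, 1, 0 gives 0.01, 0.1 and 1, which matches all three examples. Literal significant figures cannot match the third, because a non-zero x cannot have zero significant figures. 'Significant digits' therefore has to mean decimal places.

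**2. Half-limit rule with the SAP's definition of the limit.** Let L be the true assay limit and let the lowest quantified value in the database be m × L. Quantified values cannot fall below L, so m ≥ 1. The imputed value is (m × L)/2.

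| Study minimum (m × L) | Imputed value | Against the true limit |
|---|---|---|
| 1 × L | 0.5 × L | below |
| 2 × L | 1.0 × L | equal |
| 3 × L | 1.5 × L | above |
| 5 × L | 2.5 × L | above |

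The imputed value is never less than L/2, and it exceeds L whenever m > 2. If no specimen is quantified, the definition supplies no limit at all.

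**3. Overlap of the two rules.** Here x is taken as the true limit, which is the case most favourable to the half-limit rule.

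| Result | Shift rule, x − u | Half-limit rule, x/2 |
|---|---|---|
| '<0.05' | 0.05 − 0.01 = 0.04 | 0.025 |
| '<5' | 5 − 1 = 4 | 2.5 |
| '<2.0' | 2.0 − 0.1 = 1.9 | 1.0 |
| '<0.01' | 0.01 − 0.01 = 0 | 0.005 |

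The rules agree only if x − u = x/2, that is x = 2u (for example 0.02, 0.2 or 2).

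**4. Lower bound of the shift rule.** A reported x > 0 with d decimal places is a whole multiple of u, so x ≥ u and x − u ≥ 0. The minimum is exactly 0, reached when x = u ('<0.01', '<0.1', '<1').

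**5. Two separate mechanisms.** Zeros come from the shift rule. Values above the assay limit come from the definition of the limit in the half-limit rule.

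**The case against.** The strongest reply is that the rules may be complementary. The shift rule would apply when the laboratory supplies x. The half-limit rule would cover below-limit results that arrive with no x, with the study minimum as a rough fallback. The wording allows this reading, and on it the overlap disappears. The wrong definition of the limit does not. A fallback that can place a censored specimen above the limit it fell below is still wrong, and nothing in the text presents it as a fallback.

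A reader might also infer more than the documents support:

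- **Negative imputed values.** Counting literal significant figures, '<0.01' has one, and 0.01 − 0.1 = −0.09. The SAP's own zero-digit example excludes that reading, and on decimal places the minimum is 0. What remains is a mislabelled term.
- **A broken eosinophil endpoint.** One might argue that a zero makes the log of the ratio to baseline undefined. No visible text sets a log scale. Protocol 9.4.5 says the ratio is summarised descriptively, and the default statistics in SAP 4.1.1 can be computed with a ratio of 0. Nothing visible shows eosinophils reported as '<x', and a count reported as numeric 0 falls outside SAP 6.2.7. The SAP text between 4.4 and 4.7 and part of 4.1.2 are blacked out and may hold a specific rule. Any effect on this endpoint is conditional.
- **Routinely false IL-5 or IgE values.** Imputation above the limit needs a study minimum of more than twice the limit. At one or two times the limit it does not occur.

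It is also fair to say that the stakes are low. No hypotheses are tested (SAP 2), and the visible plan uses IL-5 and IgE only as baseline descriptors.

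**Conclusion.** Wrong as written, minor. The definition of the quantification limit in SAP 6.2.7 is incorrect on its face, and this conclusion needs no assumption about frequency. Its effect is an imputed value of at least half the true limit, which passes the limit once the study minimum is more than twice it. The missing precedence is a second and weaker fault, because it depends on reading the two triggers as overlapping. Where they overlap, the difference can be material for a single specimen (0.04 against 0.025, or 4 against 2.5), and the shift rule can return exactly 0.

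The visible consequence is limited to descriptive laboratory summaries, including baseline IL-5 and IgE. The number of results affected cannot be computed, because no assay limits are given. The visible text shows no effect on the primary endpoint, which is a count of flares.

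**What to change.** Amend SAP 6.2.7 in three places:

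1. Use one left-censoring rule. Any '<x' or below-limit result is set to half the limit reported by the laboratory for that assay. This value always lies above 0 and below the limit (for example 0.05 gives 0.025, and 0.01 gives 0.005).
2. Delete the explanation of the limit as the lowest observed value.
3. Keep the one-unit shift for '>x' results only, and replace 'significant digits' with 'decimal places'.

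The cost is a one-paragraph SAP edit and the matching programming change before database lock, with no effect on study conduct. The documents do not say whether each below-limit result arrives with its limit. Where one does not, the assay limit would have to be obtained from the laboratory. Protocol 10.2 assigns most tests to a central laboratory, so this should be a short request.
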